8.5 Clinical Laboratory Evaluations

All laboratory values outside the normal range will be evaluated for clinical significance by the investigator and annotated as Clinically Significant (CS) or Not Clinically Significant (NCS). Subjects with values outside of the normal range (at the screening visit) may continue in the study at the Investigator's discretion or be withdrawn for further investigation.

All the laboratory investigations will be conducted in the respective site lab while the immunogenicity test will be conducted in Laboratory at HIV Netherlands Australia Thailand Research Collaboration (HIV-NAT) (Chula CRL). The valid list of reference ranges including the

methods for all parameters of central laboratory, and quality certificates will be provided to the sponsor prior to the start of the study.

Following laboratory tests will be performed during screening, titration period [week 12/Day 84 (visit 7)], extended titration period (in substantiated cases) and end of the study.

Haematology:

- Haemoglobin
- Haematocrit
- Total White Blood Cell (WBC) count
- Differential WBC count
- Platelet count
- RBC count
- Reticulocyte count
- Mean Corpuscular Volume (MCV)
- Mean Corpuscular Haemoglobin (MCH)
- Mean Corpuscular Haemoglobin Concentration (MCHC)
- Peripheral smear

Additionally, CBC (haemoglobin, haematocrit, total WBC count, differential WBC count, platelet count and RBC count) will be performed at all the visits, reticulocyte count will be performed at visit 7 (week 12/Day 84) only during titration period and visit 16 (week 36/Day 252). Peripheral smear will be performed at visit 16 (week 36/Day 252).

Serum chemistry:

- Fasting blood glucose
- Sodium
- Potassium
- Chloride
- BUN
- Serum creatinine
- Total bilirubin
- Total protein
- ALT

- AST
- Total cholesterol
- C-Reactive Protein
- Alkaline Phosphatase
- HbA1C*

These tests will be performed during screening and end of the study visit 23 (week 64/ Day 448). Additionally, BUN (pre and post haemodialysis) will be done on visit 8 (Day 91/week 13), visit 13 (week 24/Day 168), visit 16 (week 36/Day 252), visit 19 (week 48/ Day 336) and visit 22 (week 60/ Day 420), serum creatinine, CRP, liver function test – ALT, AST and alkaline phosphatase will be performed at visit 16 (week 36/ Day 252).

*HbA1C will be done at screening visit.

Serology

- HBV (HBsAg and IgM anti-HBc) & HCV (Anti-HCV antibody)
- IgM anti-HBc is optional for Russian sites.

These tests will be performed during screening visit.

Urinalysis:

- Colour
- Transparency
- pH
- Specific gravity
- Protein
- Glucose
- Ketone bodies
- Bilirubin
- Blood
- Nitrite
- Urobilinogen
- Microscopic examination

These tests will be performed during screening and end of the study visit 23 (week 64/ Day 448).

Serum Beta HCG at screening, baseline visit (visit 8/Week 13/Day 91) and end of study visit 23 (week 64/Day 448)

Immunogenicity assessments

- Anti- epoetin Antibody by Radio Immunoprecipitation (RIP) Assay

For determination of anti-epoetin antibodies in human serum samples a RIP-assay will be employed. Serum samples for immunogenicity assessments will be collected at screening, baseline visit (visit 8/Week 13/Day 91), visit 5 (week 8/Day 56), visit 11 (week 16/Day 112), visit 13 (week 24/Day 168), visit 16 (week 36/ Day 252) and visit 23 (week 64/ Day 448).

The samples will be frozen at -80° C (for long term storage) or -20° C (for storage of 3 – 4 months) and kept until analysis in a central laboratory. In all patients, the last available blood sample will be analysed first. The last available sample for the interim analysis will be visit 16 (week 36) and for the end of the study analysis will be visit 23 (week 64/Day 448). Only if anti-epoetin antibodies are detected, all previous blood samples for the respective patient will be analysed in order to detect the time point of first occurrence.

The blood samples from the Russian centers will be shipped to the Laboratory at Chulalongkorn hospital. Blood samples of subjects who test positive for anti-epoetin antibody will be retained for lifelong years while the negative samples will be retained for one year from testing.

Apart from the above-mentioned visits, if the any of the following develop suggestive of possible antibody-mediated PRCA, the investigator can test for anti-epoetin antibody. A positive antibody test will be confirmed by bone marrow biopsy to rule of the incidence of PRCA.

- Sudden rapid decrease in haemoglobin concentration at the rate of 0.5 to 1.0 g/dl OR requirement of transfusions at the rate of approximately 1 to 2 per week, AND
- Normal platelet and white cell counts, AND
- Absolute reticulocyte counts less than 10,000/ μ L. This test will be performed with every visit when the CBC was done
- The investigational product must be temporarily withheld until the result of immunogenicity assessments is shown negative, IP can be re-started upon confirmation of negative test for immunogenicity..

Fecal occult blood test

This test will be performed during screening visit as per PI discretion

Iron study

- Serum ferritin level
- Transferrin saturation (TSAT)
- Serum iron

- Total Iron Binding Capacity (TIBC) (optional)

These tests will be performed during screening, baseline visit (visit 8/Week 13/Day 91), visit 11 (week 16/Day 112), visit 13 (week 24/ Day 168), visit 16 (week 36/Day 252), visit 19 (week 48/Day 336) and visit 23 (week 64/ Day 448).

Intact parathyroid hormone level

This test will be performed during screening visit

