3.1.6 Discontinuation Criteria

1. Subjects are free to drop out from the study at any time without stating any reason and they can choose not to receive the drug or equivalent after signing the consent. If the subject chooses not to receive the study drug after signing the consent, the subject must notify the Investigator before dispensing of the study drug. However, the subjects will continue to receive all the standard medical care, to which they are entitled.
2. Investigators may also, at their discretion, withdraw the subject from participating in the study at any time, with prior notification to the sponsor with the reason for the same.

However, subjects must be withdrawn from therapy, if any of the following events occur after giving the consent:

- a. Subject suffers from significant intercurrent illness or undergoes surgery during the course of the study where continued participation in the study presents a significant safety concern.
- b. Subject develops anti-epoetin antibodies or PRCA or severe allergic reaction
- c. Subjects requires epoetin dose more than 300 IU/kg/week
- d. Subject experiences adverse event or laboratory abnormality, when withdrawal would be in the best interest of the subject, as assessed by the investigator
- e. The subject fails to comply with the requirements of the protocol (e.g., visit window deviation) the subject may be withdrawn at the discretion of investigator and/or after discussion with medical monitor.
- f. It is necessary to further protect the health of the subject or the integrity of the study.
- g. Pregnancy.

3. The study is terminated by Sponsor, Regulatory Authorities or IEC/ IRB.

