4.2 Removal of Subjects from Therapy

4.2.1 Reasons for Withdrawal/Early Discontinuation

Any subject, who discontinues from the study treatment for any reason, will have his/her study treatment discontinuation recorded.

Subjects withdrawn prior to randomization but after signing informed consent:

- Screen Failure
- Withdrawal by Subject
- Investigator Decision

Subjects withdrawn after randomization but before completing the study as per protocol:

- Adverse Event as per PI discretion

- If subjects develop anti-epoetin antibodies or PRCA or severe allergic reaction
- If the subject requires epoetin dose more than 300 IU/kg/week
- Death
- Lost to Follow-up
- Pregnancy
- Progressive Disease
- Study Terminated by Sponsor
- Withdrawal by Subject

If a subject withdraws from the study, the investigator will complete and report the observations as thoroughly as possible up to the date of withdrawal including the date of last treatment and the reason for withdrawal.

If the subject is withdrawn due to an adverse event, the investigator will follow the subject until the adverse event has resolved or stabilized.

All subjects who are withdrawn from the study, effort should be made to complete protocol specified withdrawal procedures (Section 4.2.2).

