8.2 Expected Adverse Events

The expected adverse events with the study drug are the following:

- Local pain
- Hypertension
- Headache
- Fever
- Skin rash
- Dizziness / hypodynia
- Local swelling
- Internal fistula obstruction
- Arthralgia
- Abdominalgia
- Nausea/vomiting
- Muscle pain
- High blood viscosity
- Epilepsy
- Stuffy nose
- Thrombosis
- Cerebral hemorrhage
- Diarrhoea
- Hyperkalemia
- PRCA

Preventive action for subject developing PRCA:

- Perform Anti- epoetin Antibody test at screening visit
- All high-risk patients will be excluded as per the inclusion and exclusion criteria.

- Performing regular test of immunogenicity at visit 5, 8, 11, 13, 16 and 23 to detect development of Anti- epoetin Antibody

Corrective action for patients developing PRCA:

- If immunogenicity test is positive, the epoetin treatment will be stopped and appropriate treatment will be provided to subject including kidney transplant. Cost of treatment will be supported by sponsor.

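### Section 8.2 promises regular antibody tests with action on a positive, but section 8.5 defers the assays: in subjects who reach Visit 16 without a for-cause test, earlier samples cannot inform the withdrawal rule, and a positive at Visit 11 and/or 13 alone is not counted

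*Protocol*

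**What the plan says.** Three places in the protocol act on antibodies.

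- Section 3.1.6 lists, among the events that require withdrawal from therapy: "Subject develops anti-epoetin antibodies or PRCA or severe allergic reaction". Antibodies are named there as an alternative to PRCA, so they suffice alone.
- Section 4.2.1 repeats this among the reasons for withdrawal after randomisation: "If subjects develop anti-epoetin antibodies or PRCA or severe allergic reaction".
- Section 8.2 gives preventive actions against PRCA, "Perform Anti- epoetin Antibody test at screening visit" and "Performing regular test of immunogenicity at visit 5, 8, 11, 13, 16 and 23 to detect development of Anti- epoetin Antibody". Under corrective action it adds: "If immunogenicity test is positive, the epoetin treatment will be stopped".

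Section 8.5 fixes how the samples are handled. Sera are drawn at screening and at Visits 5, 8, 11, 13, 16 and 23, then frozen. On the order of assay it says: "In all patients, the last available blood sample will be analysed first". That sample is Visit 16 for the interim analysis and Visit 23 for the end of the study. Then: "Only if anti-epoetin antibodies are detected, all previous blood samples for the respective patient will be analysed". The stated purpose of that second step is to date the first occurrence. Section 8.5 also lets the investigator test at other times when a clinical picture suggests antibody-mediated PRCA, with product withheld until a negative result.

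The safety endpoint in section 3.1.3 counts subjects with anti-EPO antibodies and sets no visit limit. The secondary objective in section 2.1.2 concerns antibodies after at least 12 months of therapy.

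**The concern.** Section 8.2 reads as monitoring: test at each listed visit and act on a positive. Section 8.5 reads as retrospective dating: store, assay the latest sample, and go back only if something is found. The two cannot both describe what happens to the samples drawn before Visit 16.

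Two things are at stake. One is the withdrawal rule: a subject can carry antibodies at Visit 11 or 13 and stay on treatment because nobody has looked. The other is the endpoint: a positive that has gone by Visit 16 is never seen. A statistical analysis plan cannot repair the second, because it cannot analyse results that the laboratory procedure does not generate.

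**Working it through.** The protocol states no figure of its own on this point. The check uses its visit days and the section 8.5 assay rule.

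**1. Wait from draw to the subject's own Visit 16 (Day 252)**

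Formula: (252 − day of draw) / 7. Nominal days; the ±2-day windows at the two visits could move an interval by up to 4 days.

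| Sample | Day | Wait |
|---|---|---|
| Visit 5 | 56 | 196 d = 28 weeks |
| Visit 8 | 91 | 161 d = 23 weeks |
| Visit 11 | 112 | 140 d = 20 weeks |
| Visit 13 | 168 | 84 d = 12 weeks |

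These are minimum waits, since section 8.5 gives no assay date. The Visit 8, 11 and 13 figures are unchanged by extended titration if later visits shift with randomisation. The next scheduled sample after Visit 16 is Visit 23: (448 − 252) / 7 = 28 weeks later.

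**2. Which positives are found**

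Four scheduled samples follow randomisation: Visits 11, 13, 16 and 23. For a subject who gives all four, there are 2^4 − 1 = 15 patterns with at least one positive.

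- If Visit 16 or 23 is positive (12 patterns), the subject is counted. The later sample triggers any action; earlier samples only date the onset.
- If Visits 16 and 23 are both negative, the earlier sera are not assayed. That leaves 2^2 − 1 = 3 patterns: Visit 11 only, Visit 13 only, or both. Without a for-cause test, none is found.

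In no pattern does a scheduled sample from before Visit 16 trigger the rule. The 3 of 15 counts patterns; it is not a probability, and the protocol gives no rates with which to weight them.

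**3. Share of samples assayed**

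If all 264 subjects complete and none is positive: drawn 7 × 264 = 1848; assayed 2 × 264 = 528.

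**4. A separate minor point: reticulocyte counts**

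The for-cause picture in section 8.5 includes a low absolute reticulocyte count, and that bullet says the test accompanies every CBC. Section 6.2 limits the count to Week 12 in regular titration. Sections 6.4 and 6.5 list it after randomisation only at Visits 10, 16 and 23, which is 3 of the 15 CBC visits from Visit 9 to Visit 23. The haematology paragraph of section 8.5 omits Visit 10. The treatment-period cells of Table 2 did not survive in the text available and cannot settle this.

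**The case against.** The strongest defence is that the plan is not blind to antibodies. The stop sentence in section 8.2 sits under "Corrective action for patients developing PRCA", and for suspected PRCA section 8.5 allows a test at any time with product withheld. Visit 16 and Visit 23 sera are assayed in everyone who reaches them. A subject who leaves earlier has the last available sample assayed, so a positive at Visit 11 or 13 would be found if that was the last draw. Assaying the latest sample first also serves the 12-month objective. Section 1.3 calls antibody-induced PRCA very rare, and an antibody that disappears during continued treatment is a further condition.

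All of this stands, and it narrows the point. A reader might infer that the withdrawal rule has no results to work with, or that no sample before Visit 16 is assayed without a later positive. The text supports neither. What remains is clinically silent positivity before Visit 16 in subjects who get that far. There the defence fails: for-cause testing is optional and needs signs of PRCA, whereas sections 3.1.6 and 4.2.1 act on antibodies without PRCA.

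The screening sample adds little. No eligibility criterion requires a negative antibody result, and the withdrawal rule concerns subjects who develop antibodies. Only the preventive list in section 8.2 conflicts with the deferred assay there.

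Assay dates and result reporting may also sit in a laboratory manual. That could answer when a result reaches the investigator. It would not remove the condition in section 8.5 on assaying earlier samples at all.

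**Conclusion.** The point holds in this limited form and should be fixed. Followed exactly, section 8.5 does not deliver the testing that section 8.2 describes. In a subject who reaches Visit 16 without a for-cause test, a Visit 11 or 13 positive cannot inform the withdrawal rule for at least 20 or 12 weeks. If later samples are negative, it is never known and is missing from the endpoint in section 3.1.3. This rests on nominal visit days and on reading the condition in section 8.5 as a real condition rather than an order of work.

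Three further inferences are not supported:

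- **That Visit 16 results wait for the interim.** Section 9.6 places that analysis after all randomised subjects complete Visit 16, but section 8.5 does not say whether sera are assayed then or as they arrive.
- **That the co-primary endpoints are affected, or that they are not.** A silently positive subject kept on treatment contributes haemoglobin and dose data and may stay in the per-protocol set. The protocol gives nothing from which to size the effect.
- **That section 8.2 or section 8.5 is the wrong one.** The documents show only that they disagree.

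The number of positives missed cannot be estimated.

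**What to change.** Reconcile sections 3.1.6, 4.2.1, 8.2 and 8.5 on three matters: when scheduled samples are assayed, which results the withdrawal rule uses, and when an individual positive reaches the investigator. The clinical rule itself is for the sponsor. This costs wording, plus whatever assay timing the sponsor then chooses.

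For the endpoint in section 3.1.3, choose one:

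- **Assay more.** Assay the stored Visit 8, 11 and 13 sera in all subjects, and count any post-baseline positive with baseline status reported. Cost: up to 3 × 264 = 792 further assays on sera already drawn, with no new visit or blood draw. Section 8.5 allows 3 to 4 months (about 13 to 17 weeks) at −20 °C, so Visit 8 and 11 sera (23 and 20 weeks old at Visit 16) would have to be those held at −80 °C. State how long sera never assayed are kept; section 8.5 gives retention only from testing.
- **Claim less.** Restate the endpoint as antibody-positive at the assayed samples: last available, Visit 16 or Visit 23. Cost: wording only.

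Neither choice makes the withdrawal rule timely; only the reconciliation does. As a separate minor edit, make the reticulocyte schedules in sections 6.2, 6.4, 6.5 and 8.5 agree with the for-cause criterion that relies on them.

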8.6 Vital Signs

The vital signs - pulse, temperature, respiration rate, and BP (with the subject in sitting position for at least 5 minutes), data will be collected and documented at every visit. Changes to vitals from screening to end of trial will be recorded as AEs if the Investigator judges these as being clinically significant.

8.7 Electrocardiograms & Chest X-Ray

ECG and chest X ray will be performed at screening (Chest X ray performed within one year prior to screening of the subject is acceptable and need not be performed at the time of screening) and the end of the study visit [visit 23 (week 64/Day 448)]. Chest X ray will be performed at visit 16 (week 36/Day 252) also.

8.8 Physical Findings

The physical examination, data will be collected and documented at every visit. Changes to physical examination from screening to end of trial will be recorded as AEs if the Investigator judges these as being clinically significant.

8.9 Other Safety Assessments

The most frequent adverse drug reaction during treatment with epoetin is a dose-dependent increase in blood pressure or aggravation of existing hypertension. Special care should be taken to closely monitor and control blood pressure in subjects treated with epoetin. If blood pressure is difficult to control after initiation of appropriate measures, the dose of epoetin should be reduced or temporarily withheld until haemoglobin begins to decrease. An increased incidence of thrombotic vascular events has been observed in patients receiving epoetin. These include venous and arterial thrombosis and embolism (including some with fatal outcomes), such as deep venous thrombosis, pulmonary emboli, retinal thrombosis and myocardial infarction.

Hence adverse events of specific interest include hypertension/aggravation of hypertension and thromboembolic events.

9 STATISTICAL METHODS

9.1 Analysis Sets

Three cohorts will be considered for the analysis: The modified intention-to-treat (mITT) cohort, per protocol (PP) and safety cohort. Per-Protocol cohort population will be considered as primary population for analysis of efficacy.

Modified Intention-to-treat Cohort:

All randomized subjects who receive study medication, have a baseline and at least one post-treatment measurement will be included in the MITT Cohort.

Per-protocol Cohort:

All randomized subjects who complete both the baseline visit and end of treatment visit and who have no major protocol violations will be included in the PP population. Subjects with major protocol violations will be excluded from this cohort.

Detailed description of what constitutes a protocol violation will be defined in the SAP.

Safety Cohort:

All subjects who are randomized at baseline visit will be included in the safety analyses for safety endpoints.

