6.5 End of Treatment / Study

Visit 23: End of study visit Week 64/ Day 448

- Demographic data (body weight: pre and post hemodialysis)
- Vital signs
- Physical examination
- Adverse events
- Concomitant medication
- Laboratory investigations (haematology, serum chemistry, urinalysis* and iron study and reticulocyte count) (refer Table in Appendix I)
- Chest X ray, ECG
- Serum Pregnancy Test (for all females of childbearing potential)
- Immunogenicity testing for anti-EPO antibody
- BUN (pre-and post Dialysis)
- Adequacy of dialysis measurement by Kt/V formula

*= Urinalysis test will be considered as optional for CKD patients as CKD patients may not be able to provide sufficient urine volume for urinalysis test due to low urine output.

Table 2: Study Visit Plan

S No .	Procedures	Screen ing	Titration period							Extend ed Titrati on period	Baseli ne*	Treatment Period												End of Study		
		V 0 (Day - 31 to Day 0)	V 1 (Wk 1/ Day 1)	V 2 (Wk 2/D ay 14)	V 3 (Wk 4/Da y 28)	V 4 (Wk 6/D ay4 2)	V 5 (Wk 8/Day 56)	V 6 (Wk 10/Da y 70)	V 7 (Wk 12/D ay 84)			V 8 (Day 91/ Week 13)	V 9 (Wk 14/ Day 98)	V 10 (Wk 15/ Day 105)	V 11 (Wk 16/ Day 112)	V 12 (Wk 20/ Day 140)	V 13 (Wk 24/ Day 168)	V 14 (Wk 28/ Day 196)	V 15 (Wk 32/ Day 224)	V 16 (Wk 36/ Day 252)	V 17 (Wk 40/ Day 280)	V 18 (Wk 44/ Day 308)	V 19 (Wk 48/ Day 336)	V 20 (Wk 52/ Day 364)	V 21 (Wk 56/D ay 392)	V 22 (Wk 60/ Day 420)
1	Informed Consent	X																								
2	Demographic Data ¹	X		X	X	X	X	X	X															X	X	
3	Medical History	X																								
4	Menstrual and Reproductive History	X																								
5	Physical/Clinical Examination ²	X		X	X	X	X	X	X															X	X	
6	Vital signs ³	X		X	X	X	X	X	X															X	X	
7	Inclusion & Exclusion Criteria	X																								
8	Eligibility Criteria											X														
9	Concomitant Medication ⁴	X		X	X	X	X	X	X															X	X	
10	Peripheral smear	X			X		X		X																	X
11	Complete Blood Count	X		X	X	X	X	X	X															X	X	
12	Reticulocyte Count	X							X	X																X
13	Renal Function (BUN)	X										X													X	X
14	Iron study	X						X				X												X		X
15	CRP																									X
16	Liver Function Test ⁵																									X
17	Serum Chemistry	X																								X
18	HbA1C	X																								X
19	Urinalysis ⁶	X																								X
20	Serology	X																								X

21	Fecal occult¹⁰ blood test & intact parathyroid hormone	X																						

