9.2 General Statistical Considerations

Analysis for all efficacy endpoints using the PP population will be the primary approach for analysis. Secondary analysis will be performed using the mITT population. For safety endpoints using the safety cohort will be the primary approach for analysis.

The SAS® package (SAS® Institute Inc., USA, and Version 9.2 or higher) will be used for statistical evaluation.

Descriptive statistics, such as mean, standard deviation, median, minimum and maximum values will be provided for the continuous variables and the number of observations and percentage will be provided for the categorical variables.

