10.9 Protocol Deviations and Violations: Condition where the Study will be terminated

After a subject is enrolled into the trial and is noticed to be noncompliant with inclusion and exclusion criteria, the same will be documented as a protocol violation(s). During the conduct of the trial process if deviation(s) are noticed from the norm mentioned in the protocol, the same will be documented as protocol deviation(s).

The severity of the protocol violation and protocol deviation will be graded as minor if the violation/deviation is not altering the integrity of the study plan or its safety and efficacy outcome, as major if the violation/deviation is altering the integrity of the study plan or its safety and efficacy outcome.

Sponsor reserves the right to terminate the study at any time and bears the responsibility for informing applicable regulatory authorities. Whereas the principal investigator reserves the right to discontinue the study for safety reasons at any time and bears the responsibility to inform the IEC. The reason for this termination will be provided to the subjects.

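### Equivalence is decided on the per-protocol set alone, which can drop subjects with a valid 6-month value, and no rule covers disagreement with the mITT result

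*Protocol*

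**What the plan says.** Section 9.1 names the deciding set: "Per-Protocol cohort population will be considered as primary population for analysis of efficacy". Section 9.2 repeats it: "Analysis for all efficacy endpoints using the PP population will be the primary approach for analysis". The only role given to the other efficacy set is in the next sentence of 9.2: "Secondary analysis will be performed using the mITT population".

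The sets are defined in 9.1:

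- PP: "All randomized subjects who complete both the baseline visit and end of treatment visit and who have no major protocol violations".
- mITT: "All randomized subjects who receive study medication, have a baseline and at least one post-treatment measurement".

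Section 9.1 does not date the end of treatment visit. The only visit listed under the End of Treatment / Study heading (6.5) is "Visit 23: End of study visit Week 64/ Day 448". Section 10.9 grades a violation or deviation "as major if the violation/deviation is altering the integrity of the study plan or its safety and efficacy outcome"; section 6.6 has the same grading. The detailed description of violations is left to the SAP.

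Section 9.4.1 compares the 95% CIs for change from baseline to 6 months with ±0.5 g/dl for haemoglobin and ±45 IU/kg/week for dose. It does not mention mITT. Section 9.6 applies the section 9 analysis once all randomised patients have completed Week 36, and the resulting report is meant to support local registration.

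**The concern.** An equivalence claim rests on a between-arm difference that randomisation protects. Once subjects are removed for reasons arising after randomisation, that protection is weakened. The usual safeguard is to ask that the PP and the mITT analyses lead to the same conclusion, because neither is reliably conservative when the aim is to show similarity: PP may be selected, and mITT may be diluted by departures from protocol.

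Here there is no such safeguard. If the PP interval lies inside a margin and the mITT interval does not, the protocol as written still yields equivalence. If the reverse happens, equivalence fails. The PP definition adds two specific exposures. A subject measured at 6 months who stops during the second half of treatment is dropped from a 6-month comparison. And whether a departure counts as major depends partly on its effect on the outcome being analysed.

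**Working it through.** The protocol gives no figure for how many subjects fall outside PP, so there is no stated number to reproduce. The check sets the definitions side by side and then asks when the gap matters.

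**Step 1. The timing mismatch.** Section 3.1.5 puts the efficacy period at weeks 13 to 39. Section 9.6 uses Week 36 for the 6-month equivalence analysis. Completion for PP is at Week 64.

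- From Week 39: 64 − 39 = 25 weeks.
- From Week 36: 64 − 36 = 28 weeks.

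PP therefore requires about six further months of participation after the co-primary value has been obtained. At the Week 36 analysis, subjects who have not yet reached Week 64 cannot meet the definition.

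**Step 2. Who enters which 6-month comparison.** Section 9.2.1 allows no imputation of efficacy data. For randomised, dosed subjects with a baseline and at least one later measurement:

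| Group | 6-month value | In the PP analysis | Contributes to the mITT 6-month analysis |
|---|---|---|---|
| A. Withdraws before 6 months | No | No | No (no imputation) |
| B. Leaves between 6 months and Week 64 | Yes | No | Yes |
| C. Completes Week 64 with a major violation | Yes | No | Yes |
| D. Completes Week 64 without a major violation | Yes | Yes | Yes |

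PP decides on D. The mITT comparison uses B, C and D. The two analyses differ only by B and C.

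**Step 3. When the gap biases the result.** In one arm, among subjects with a 6-month value, let p be the share in B or C, and let d be their mean change minus the mean change in D. Ignoring covariate adjustment:

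- mITT mean = PP mean + p × d
- mITT treatment difference − PP treatment difference = p(EPIAO) × d(EPIAO) − p(EPREX) × d(EPREX)

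This is zero if the excluded subjects resemble the retained ones (d = 0 in both arms), or if the two products are equal. It is non-zero only if exclusion is related to outcome and the relation or the rate differs between arms.

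**Step 4. Check of the harmless case.** A simulation used 132 per arm, normal data, assumed dose SDs of 60, 80 and 104 IU/kg/week, a true difference equal to the 45 IU/kg/week margin, and 5% or 18% of each arm removed without regard to outcome. Each setting had 4,000 runs. Equivalence was falsely declared in 2.3% to 2.9% of trials, against a nominal 2.5%. Exclusions unrelated to outcome cost numbers but do not inflate the error.

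**Step 5. Is p or d available?** No. Section 9.8 gives a drop-out rate of about 18%, not split by time, so it mixes A and B and contains no rate for C. No SD and no arm-specific rate is given. The size of the gap cannot be calculated from the protocol.

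**The case against.** The strongest reply has four parts.

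*PP as the primary set is not an error in an equivalence trial.* That stands. The fault is narrower: PP decides alone, with this definition, and nothing is said about disagreement.

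*mITT is pre-specified, so a discrepancy would be visible, and the SAP may settle its interpretation.* This stands in part. Section 9.1 leaves the violation list to the SAP, which is not at hand and could add a rule. But the protocol itself fixes which set decides, and seeing a discrepancy does not change the conclusion under 9.4.1.

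*The end of treatment visit might mean the end of the 26-week efficacy period.* The text does not exclude this, but the only visit under that heading is Week 64, so the wording needs correcting on either reading.

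*The bias is conditional.* That stands, as Step 3 shows.

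Two stronger readings are tempting and not supported. First, a reader might infer from the 18% drop-out that about one subject in five separates the deciding set from mITT. Drop-outs before 6 months are missing from both comparisons, so the 18% does not measure the gap.

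Second, section 3.1.6 requires withdrawal for "Subjects requires epoetin dose more than 300 IU/kg/week", and a reader might infer that PP hides a large dose difference. If 3% to 10% more EPIAO than EPREX subjects crossed 300 from a starting dose of 100 to 150, the omitted difference would run from 0.03 × 150 = 4.5 to 0.10 × 200 = 20 IU/kg/week. From a starting dose of 250 it would run from 0.03 × 50 = 1.5 to 0.10 × 50 = 5. Only the 300 is in the protocol; the excess and the starting doses are assumptions. Moreover, subjects withdrawn before 6 months would normally be absent from the mITT comparison too, so agreement between the sets would not reveal the effect.

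**Conclusion.** The point holds as a modest but real weakness. Sections 9.1, 9.2 and 9.4.1 let PP alone decide equivalence, and that set can discard subjects who have a valid 6-month value, either because they did not reach Week 64 or because a departure was graded major. The same analysis feeds the Week 36 report intended for registration.

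No size is claimed. Bias arises only if exclusion is related to outcome and acts differently in the two arms, and the protocol gives no rates or SDs from which to judge either. A reader might also infer that exclusions would favour the sponsor. The documents show no mechanism for that: section 5.1.6 keeps investigators and most study staff blinded, and Step 3 allows a shift in either direction.

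The conclusion rests on two readings: that the end of treatment visit is Visit 23 at Week 64, and that no concordance rule exists outside the protocol.

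**What to change.** In 9.1, 9.2 and 9.4.1:

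1. State that equivalence is concluded only if, for each co-primary endpoint, the 95% CI lies within its acceptance range in both the PP and the mITT population.
2. State that the mITT analysis uses every available 6-month value of randomised, dosed subjects, regardless of protocol departures.
3. Define PP completion for the co-primary endpoints by the visit that supplies the 6-month value, named explicitly, instead of Week 64. This also lets the PP set be formed at the Week 36 analysis.

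The cost is a few sentences and no new data. The probability of success falls slightly, because intervals in two sets must pass. No multiplicity adjustment is needed, since all must pass. Item 3 can only keep or add subjects in PP.

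The change brings groups B and C of Step 2 into the decision. It does not recover group A, because section 9.2.1 allows no imputation; early withdrawal needs its own missing-data provision.
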